		CYCLE 1 21 days				CYCLE 2 21 days	CYCLES ≥3 (21 days per cycle)	END of TREATMENT (EOT)/ FOLLOW-UP		
Visit Identifier ^a	Screening ¹ (≤28 days)	Day 1	Day 5	Day 8	Day 15	Day 1	Day 1	End of Treatment/ Withdrawal ²⁶	Post-Treatment Follow-Up ²⁷	Survival Follow-Up ²⁸ (every 4 months up to 3 years, then every 6 months)
Visit Time Window (days)	N/A		±3	±1	±1	±2	±2	±3	±7	±7
Other Clinical Assessments										
Serious and non-serious adverse event monitoring ²¹	X	X	→			→	→	→	→	
Concomitant medications and treatments ²²	X	X	→			→	→	→	→	X (subsequent systemic anticancer treatment)
Mood assesment ²³		X				X	X (up to Cycle 6 and then Day 1 of every other cycle)	X		
Suicidal Ideation and Behavior ²⁴		X				X	X (up to Cycle 6 and then Day 1 of every other cycle)	X		
Survival status ²⁸										X
Other Samples										
Pharmacokinetic Sampling ²⁵	See footnote ²⁵									

a. Day relative to start of study treatment (Day 1 of Cycle 1).

Abbreviations: → = ongoing/continuous event; ECG = electrocardiogram; ECOG = Eastern Cooperative Oncology Group; LVEF = left ventricular ejection fraction; MUGA = Multigate acquisition; CT = computed tomography; MRI = Magnetic Resonance Imaging; EORTC = European Organization for Research and Treatment of Cancer; ICR= Independent Central Radiology; PD = Progression of Disease; ALK = anaplastic lymphoma kinase; PE = Physical examination; CTCAE = Common Terminology Criteria for Adverse Events; HBV = Hepatitis B Virus; HCV = Hepatitis C Virus; QD = Quaque Die (every day); CCI N/A = Not applicable.

Footnotes:

Acceptable time windows for performing each assessment are described in the column headers.

1. Screening: To be obtained within 28 days prior to enrollment (Cycle1Day1: C1D1). Available results for assessments that have been performed prior to informed consent being obtained as part of the patient's on-going routine standard of care testing (laboratory tests or tumor imaging scans) may be used to satisfy patient eligibility assessment, provided they have been performed within the required timing (that is 7 days prior enrollment for laboratory tests or 28 days prior enrollment for tumor imaging or 6 weeks prior enrollment for bone scan [or bone MRI if preferred by investigator]) and meet the related criteria.
2. Informed Consent: Must be obtained prior to undergoing any study-specific procedures. CCI [REDACTED]

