5.3.1. Missing Dates

For purposes of data listings, dates will reflect only the information provided by the investigator on the CRF.

If start dates for adverse events or concomitant medications are completely missing a worst case approach will be taken whereby the events will be considered treatment emergent and the medications will be considered concomitant. If only partial information are available (eg, only a month and year or only a year) and the partial information provide sufficient information to indicate the dates are prior to the start of study treatment (eg, month/year less than month/year of first dose) then these will be considered to have started prior to treatment; otherwise a similar worst case approach will apply and these will be considered to have started after treatment.

Date of Last Dose of Study Treatment

No imputation will be done for first dose date. Date of last dose of study treatment, if unknown or partially unknown, will be imputed as follows:

- If the last date of study treatment is completely missing and there is no End of Treatment (EOT) CRF page and no death date, the patient should be considered to be ongoing and use the data cutoff date for the analysis as the last dosing date; or
- If the last date of study treatment is completely or partially missing and there is EITHER an EOT CRF page OR a death date available (on or prior to the data cutoff date), then impute this date as the last dose date:

= 31DECYYYY, if only Year is available and Year < Year of min (EOT date, death date),

= Last day of the month, if both Year and Month are available and Year = Year of min (EOT date, death date) and Month < the month of min (EOT date, death date), or

= min (EOT date, death date), for all other cases.

Missing or Partial Death Dates

Missing or partial death dates will be imputed based on the last contact date:

- If the entire date is missing it will be imputed as the day after the date of last contact (see derivation of date of last contact in [Section 5.2.7](#)); or

If the day or month is missing, death will be imputed to the maximum of the full (non-imputed) day after the date of last contact and the following:

Missing day: 1st day of the month and year of death, or

Missing day and month: January 1st of the year of death.

Date of Start of New Anti-cancer Therapy

Incomplete dates for new anti-cancer therapy will be imputed as follows and will be used to determine censoring dates for efficacy analyses:

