- The end date of new anti-cancer therapy will be included in the imputation for start date of new anti-cancer therapy. If the end data of new anti-cancer therapy is:
 - Completely missing then it will be ignored in the imputations below,
 - Partially missing with only year available then the imputations below will consider 31DECYYYY as the end date of the new anti-cancer therapy, or
 - Partially missing with only month and year available then the imputations below will consider the last day of the month for MMMYYYY as the end date of the new anti-cancer therapy.
- For patients who have not discontinued study treatment at the time of the data cutoff date, last dose of study treatment is set to the data cutoff date in the imputations below.
- If the start date of new anti-cancer therapy is completely or partially missing then the imputed start date of new anti-cancer therapy is:
 - = 31DECYYYY, if only Year is available and Year < Year of min [max (PD date + 1, last dose of study treatment + 1), end date of new anti-cancer therapy]
 - = Last day of the month, if both Year and Month are available and
 - Year = Year of min [max (PD date + 1, last dose of study treatment + 1), end date of new anti-cancer therapy]
 - Month < Month of min [max (PD date + 1 day, last dose of study treatment + 1 day), end date of new anti-cancer therapy]
 - = min [max (PD date + 1, last dose of study treatment + 1), end date of new anti-cancer therapy], for all other cases.

AE Onset Date:

The following imputation rules apply if the event is unique for a patient or it is the first of a series of similar events; otherwise, the AE Onset Date will not be imputed:

- If the AE Collection Date is not missing, is less than the Date of First Exposure to Treatment, and is less than the AE Stop Date, then AE Onset Date is set to the Date of AE Collection.
- If the Previous Visit Date is greater than the Date of First Exposure to Treatment and less than the AE Stop Date, the AE Start Date is set to the previous visit date.

- If the Date of First Exposure to Treatment is greater than the previous visit date and less than the AE Stop Date, the AE Onset Date is set to the Date of First Exposure to Treatment.
- Otherwise AE Onset date is set to the AE Stop date.

AE Stop Date:

Ongoing events will have the AE Stop Date set to one of the following values:

- Date of Death, if the patient died and a date of death exists.

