- Maximum of (Patient Withdraw date, AE Onset Date, AE Collection Date) if the patient withdrew from the study and a date of withdraw exists.
- Maximum of (AE Onset Date, Subject Summary Collection Date, AE Collection Date) if the Disposition CRF page exists but a date of withdraw does not exist.
- Maximum of (Last Treatment Date, AE Onset Date) if no Disposition page exists.

Imputation will only occur if event is unique for the patient, or it is the last of a series of similar events; otherwise the Stop Date will not be imputed. Adverse Events are deemed similar if they have the same verbatim term.

Resolved events will have the AE Stop Date set to the maximum of the AE collection date and the AE Onset date.

Other Missing or Partial Dates

Imputation methods for other partial dates as follows:

- If the day of the month is missing for a start date used in a calculation, the first day of the month will be used to replace the missing date.
- If both the day and month are missing, the first day of the year is used.
- For stop dates, the last day of the month, or last day of the year is used if the day or day and month are missing, respectively.
- If the date is completely missing, no imputation will be performed.

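### SAP 5.3.1 has no AE onset rule for a previous visit on the first-dose date, so a missing onset of an early event defaults to its stop date

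*SAP*

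**What the plan says.** SAP 5.3.1, under AE Onset Date, states its scope: "The following imputation rules apply if the event is unique for a patient or it is the first of a series of similar events". Four rules follow.

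- **Rule 1.** An event collected before first exposure, and before its stop date, takes the collection date as onset.
- **Rule 2.** "If the Previous Visit Date is greater than the Date of First Exposure to Treatment and less than the AE Stop Date", onset is the previous visit date.
- **Rule 3.** "If the Date of First Exposure to Treatment is greater than the previous visit date and less than the AE Stop Date", onset is the date of first exposure.
- **Fallback.** "Otherwise AE Onset date is set to the AE Stop date".

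The same section treats status separately: "If start dates for adverse events or concomitant medications are completely missing a worst case approach will be taken", under which such an event counts as treatment emergent. For ongoing events the stop date is itself imputed: to the date of death if there is one, otherwise by rules such as "Maximum of (Last Treatment Date, AE Onset Date) if no Disposition page exists".

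SAP 6.5.1.1 computes time to onset and duration of adverse events of special interest from these start and stop dates. Note a to the Protocol's Schedule of Activities defines the visit identifier as "Day relative to start of study treatment (Day 1 of Cycle 1"), so the Day 1 visit normally falls on the first-dose date.

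**The concern.** Rules 2 and 3 are mirror images, and both are strict. When the previous visit and first exposure share a date, neither is met. Rule 1 is not met either, because the event was collected after dosing began. Only the fallback remains.

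This tie is the ordinary configuration for an event first reported at the contact that follows Cycle 1 Day 1. An event that began in the first days of treatment is then dated to its end. At stake are the time-to-onset and duration summaries for events of special interest, which include the CNS mood, speech and cognition events (SAP 3.5.2). An early, lasting event would be summarised as late and lasting one day.

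**Working it through.** The plan states no figure on this point, so the check is to run the rules on dates.

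**Inputs.** First exposure F = study day 1 (SAP 5.2.3). P = previous visit, C = collection date, S = stop date. From SAP 6.5.1.1, time to onset = onset − first dose + 1, and duration = stop − onset + 1.

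**Tied case.** P = 1, C = 8 (Cycle 1 Day 8 visit), S = 60, and the Day 5 contact not counted as a visit.

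1. Rule 1 needs C < F: 8 < 1 is false.
2. Rule 2 needs P > F: 1 > 1 is false.
3. Rule 3 needs F > P: 1 > 1 is false.
4. Fallback: onset = Day 60. Time to onset = 60 − 1 + 1 = 60 days; duration = 60 − 60 + 1 = 1 day.

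The imputed onset lies 60 − 8 = 52 days after the event was reported. If the event began between the two visits, its onset is between Day 1 and Day 8 and its duration between 60 − 8 + 1 = 53 and 60 − 1 + 1 = 60 days.

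**Same case with rule 2 as P ≥ F.** 1 ≥ 1 and 1 < 60 both hold, so onset = Day 1, time to onset = 1 day and duration = 60 days.

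**Other stop days, same tie**

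| Stop day | As written: time to onset / duration | With ≥: time to onset / duration | Shift in onset (S − 1) |
|---|---|---|---|
| 3 | 3 / 1 | 1 / 3 | 2 |
| 15 | 15 / 1 | 1 / 15 | 14 |
| 43 | 43 / 1 | 1 / 43 | 42 |
| 60 | 60 / 1 | 1 / 60 | 59 |
| 127 | 127 / 1 | 1 / 127 | 126 |

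**Neighbouring cases, stop Day 43.** Collected on Day 1 after a screening visit on Day −7, rule 3 gives onset Day 1 and duration 43. Collected on Day 15 after a Day 8 visit, rule 2 gives onset Day 8 and duration 43 − 8 + 1 = 36. Only the tied case between them goes to the end of the event.

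**Is the tie the only gap?** The rules were run for previous visits from Day −28 to Day 59, stop dates from Day 2 to Day 119 that fall after the previous visit, and collection up to Day 69, after both first dose and the previous visit.

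| Previous visit | Combinations | Rule used as written | Rule used with ≥ in rule 2 |
|---|---|---|---|
| Before first exposure | 224,672 | 3 | 3 |
| On first exposure | 8,024 (118 stop days × 68 collection days) | Fallback | 2 |
| After first exposure | 213,875 | 2 | 2 |

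These are counts of date combinations, not of patients. Within this range the tie is the only gap, and the operator change alters nothing else.

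**Ongoing event, patient died.** The stop date is the date of death and needs no onset date, so in the tie the fallback sets onset to the date of death.

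**The case against.** Several limits stand.

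- Previous Visit Date is not defined. The schedule has a Cycle 1 Day 5 contact (±3 days). If that counts as a visit and takes place on Day 5, an event reported on Day 8 has P = 5, and rule 2 gives onset Day 5 and, for stop Day 60, duration 60 − 5 + 1 = 56 days. The tie then covers only events reported at the Day 5 contact itself.
- Protocol 5.1 lets treatment start one day after the allocation it calls randomization. If the Day 1 visit precedes first dose by that day, rule 3 works.
- For a resolved event with no recorded stop date, SAP 5.3.1 uses the later of collection and onset. With collection on Day 8 and onset missing, stop and onset both become Day 8, which is inside the plausible range.
- The summaries are descriptive, and imputed values are flagged (SAP 5.3).

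A reader might also draw stronger conclusions that the documents do not support.

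- *That the rule reverses the SAP's worst-case approach.* That approach decides only whether an event is treatment emergent or a medication concomitant. It makes no commitment to early onset or long duration.
- *That every error is large.* Relative to the corrected rule the shift is S − 1 days, so a short event is barely misdated.
- *That an ongoing event in a patient treated for 8 months gets an onset near Day 244* (8 × 30.4375 = 243.5). The 8 months in SAP section 2 is the estimated time from the last subject's first dose to data cutoff, not a treatment duration. The stop rule needed applies only without a Disposition page and takes the onset date as an input, so it is circular when onset is missing. SAP 6.5.1.1 also censors the duration of ongoing events at the last on-treatment visit.
- *That rule 1 conflicts with the worst-case default.* Rule 1 is the specific provision and gives a sensible date to an event already reported before dosing. Declaring all such events not treatment emergent would ignore Protocol 9.5.1, which counts an increase in severity after first dose.

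**Conclusion.** The gap is real and minor. When the previous visit date equals the first exposure date, a missing onset is set to the stop date. For a resolved event of special interest with a known stop date, time to onset then equals the stop day and duration is 1 day. For an ongoing event in a patient who died, onset is the date of death.

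Only the SAP 6.5.1.1 time-to-onset and duration summaries are affected, and only for unique or first-in-series events with a missing onset. In a subgroup of n patients, one event stopping on Day 60 moves the mean time to onset by 59/n days. Treatment-emergent status is largely protected by the separate missing-start rule. It could be lost if status were instead derived from an imputed onset that falls after new anti-cancer drug therapy begins (SAP 3.5). No efficacy result is involved.

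The conclusion assumes a literal reading of the inequalities and a Day 1 visit on the first-dose date. The documents give no count of missing onsets; that it is small is an assumption, and it could be zero.

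**What to change.** In SAP 5.3.1, change rule 2 so that the previous visit date is 'greater than or equal to' the date of first exposure. Define Previous Visit Date, and say whether the Cycle 1 Day 5 contact counts.

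The fallback can stay. Once rule 2 includes equality, an event with known dates that rule 1 does not cover reaches the fallback only when its stop date is on or before the later of first exposure and previous visit, and the stop date is then a reasonable choice. The treatment-emergent definition needs no change.

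The cost is a few words in the SAP, one definition and one comparison operator in the program. No data collection changes.

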5.3.2. Missing Toxicity Grade of Adverse Events

Prior to Study Treatment: If no toxicity grade is available or the grade is reported as unknown for an adverse event prior to the first study treatment, then Grade 1 will be assumed for purposes of defining a baseline grade for assessing if further occurrences are treatment emergent. However, if the patient experiences multiple episodes of the same AE prior to

study treatment, then the maximum toxicity grade observed prior to study treatment will be utilized in assessing if further occurrences are treatment emergent.

During Study Treatment: If no toxicity grade is available or the grade is reported as unknown for an adverse event during the study treatment, then the event will be considered treatment emergent unless a baseline event was reported as Grade 4.

In summaries which present maximum toxicity grade, the maximum of non-missing grades will be displayed. Missing grade will only be displayed for cases where a patient reported only one event and the grade is missing.

5.3.3. Missing Pharmacokinetic (PK) data

Concentrations below the limit of quantification

For all calculations, figures, and estimation of individual pharmacokinetic parameters, all concentrations assayed as below the level of quantification (BLQ) will be set to zero. In log-linear plots these values will not be represented. The BLQ values will be excluded from calculations of geometric means and their confidence intervals. A statement similar to 'All values reported as BLQ have been replaced with zero' should be included as a footnote to the appropriate tables and figures. In listings BLQ values will be reported as below limit of quantification (" $<LLOQ$ "), where LLOQ will be replaced with the corresponding value from the analytical assay used.

Deviations, Missing Concentrations and Anomalous Values

In summary tables and plots of median profiles, concentrations will be set to missing if one of the following cases is true:

- A concentration has been reported as ND (ie, not done) or NS (ie, no sample);
- A deviation in sampling time is of sufficient concern or a concentration has been flagged as anomalous by the clinical pharmacologist.

Summary statistics will not be presented at a particular timepoint if more than 50% of the data are missing. For analysis of pharmacokinetic concentrations, no values will be imputed for missing data.

Actual PK sampling times will be used in the derivation of PK parameters. If a PK parameter cannot be derived from the concentration data, the parameter will be coded as NC (ie, not calculated). NC values will not be generated beyond the day that a patient discontinues.

In summary tables of concentration-time profiles or PK parameters, statistics will be calculated by setting NC values to missing; and statistics will not be presented for the treatment if more than 50% of the data are not collected, not calculated, or below LLOQ. For statistical analyses (ie, analysis of variance), PK parameters coded as NC will also be set to missing.

If an individual patient has a known biased estimate of a PK parameter (due for example to a deviation for the assigned dose level), this will be footnoted in summary tables and will not be included in the calculation of summary statistics or statistical analyses.

5.3.4. Missing ECG Data

For ECG analyses, no values will be imputed for missing data (except RR values that can be derived from HR values, if present. If both RR and HR values are missing QTcB will not be determined). In case of missing RR value, RR (msec) will be derived as $(60/HR \text{ (bpm)}) * 1000$, if HR is collected.

If one or two of the triplicate measurements for an ECG parameter are missed, the average of the remaining two measurements or the single measurement can be used in the analyses. If all triplicate measurements are missing at a timepoint for an ECG parameter, no values will be imputed for this timepoint. If the triplicate needs to be repeated because of an artifact, then the repeated triplicate will be reported on an unscheduled CRF page. Based on a review of the data these unscheduled assessments may be used in place of the assessments at the nominal time. Data review and consultation with the study team is required to flag these cases.

CCI
[REDACTED]

6. ANALYSES AND SUMMARIES

All efficacy analyses will be performed by Cohort on the SA set.

Radiographic images and clinical information collected on study will be reviewed by an ICR. ICR assessment will be used for the primary analysis of OR and for all secondary endpoints based on radiological assessments of tumor burden (ie, IC-OR, DoR, IC-DoR, TTR and PFS). These endpoints will also be derived using the local radiologist's/investigator's assessment.

6.1. Primary Endpoint(s): Objective Response in Cohort 1

The primary efficacy analysis will evaluate the anti-tumor effect of lorlatinib as a single agent as measured by OR per RECIST v1.1 in locally advanced or metastatic ALK-positive NSCLC patients whose disease has progressed after crizotinib treatment.

OR is defined as a complete response (CR) or partial response (PR) recorded from enrollment until disease progression or start of new anti-cancer therapy. Both CR and PR must be confirmed by repeat assessments performed no less than 4 weeks after the criteria for response are first met.

Objective Response Rate (ORR) is defined as the percentage of patients with a best overall confirmed response of CR or PR according to RECIST v1.1 relative to the total patients in the analysis population. Patients without documented CR or PR will be considered as non-responders. Additionally, patients with inadequate data for tumor assessment (eg, no baseline assessment or no follow-up assessments) will be considered as non-responders. The primary evaluation of ORR will be based on ICR's review relative to the SA set.

The exact test will be performed to test the null hypothesis $H_0: ORR \leq 30\%$. One-sided p-value will be provided together with the estimate of ORR and the corresponding exact 95% CI.

Best overall response (BOR) will be assessed based on reported overall responses at different evaluation timepoints by the independent radiologist and by the investigator from the date of first dose until documented disease progression or start of new anti-cancer therapy, according to the following rules:

- CR = at least two determinations of CR at least 4 weeks apart and documented before progression and start of new anti-cancer therapy.
- PR = at least two determinations of PR or better (and not qualifying for a CR) at least 4 weeks apart and before progression and start of new anti-cancer.
- SD (for patients with at least one measurable lesion at baseline) = at least one SD assessment (or better and not qualifying for CR or PR) ≥ 6 weeks after date of first dose and before progression and the start of new anti-cancer therapy.
- Non-CR/Non-PD (for patients with only non-target disease at baseline) = at least one Non-CR/Non-PD assessment (or better and not qualifying for CR or PR) ≥ 6 weeks after date of first dose and before progression and the start of new anti-cancer therapy.
- PD = progression ≤ 14 weeks after date of first dose and not qualifying for CR, PR or SD.
- Not Evaluable (NE) = all other cases.

Clinical deterioration will not be considered as documented disease progression.

Patients with BOR of NE will be summarized by reason for having NE status. The following reasons will be used:

- Early death defined as death prior to 6 weeks after date of first dose;
- No post-baseline assessments, for reasons other than early death;
- All post-baseline assessments have overall response NE;
- New anti-cancer therapy started before first post-baseline assessment;

- SD of insufficient duration (<6 weeks after first dose);
- PD too late (>14 weeks after first dose).

Special and rare cases where BOR is NE due to both early SD and late PD will be classified as 'SD of insufficient duration'.

The frequency (number and percentage) of patients with BOR of CR, PR, SD, PD, non-CR/non-PD (applicable only to patients with non-measurable disease at baseline), and NE (not-evaluable) will be tabulated.

Waterfall plots displaying the best percentage change from baseline in tumor size will be presented. The best percent change from baseline will be calculated from start of study treatment up to first visit with disease progression or to the last visit available prior to the start of new anti-tumor therapy (for patients who start new anti-tumor therapy prior to progression or who are progression-free patients at the time of analysis).

A spider plot displaying the % change from baseline across visits in tumor size will be presented. The % change from baseline will be calculated from start of study treatment to each visit up to first visit with disease progression or to the last visit available prior to the start of new anti-tumor therapy (for patients who start new anti-tumor therapy prior to progression or who are progression free patients at the time of analysis).

